Primary Objective: To evaluate the effect of AMG 334 compared to placebo on the change from baseline in mean monthly migraine days, in subjects with episodic migraine

Secondary Objectives:

Efficacy:

- To evaluate the effect of AMG 334 compared to placebo on the proportion of subjects with at least 50% reduction from baseline in mean monthly migraine days
- To evaluate the effect of AMG 334 compared to placebo on the change from baseline in mean monthly acute migraine-specific medication treatment days

Safety: To evaluate the safety and tolerability of AMG 334

Clinical Home Use Substudy (During the Open-label Treatment Phase [OLTP]) Objectives:

- **Primary Objective:** To assess users' ability to administer a full dose (140 mg) of AMG 334 in home-use, using either 2 pre-filled 70 mg/mL autoinjectors/pens (AIs/pens) or 1 pre-filled 140 mg/mL AI/pen
- **Secondary Objective:** To assess the safety and tolerability of AMG 334 administered using either 2 pre-filled 70 mg/mL AIs/pens or 1 pre-filled 140 mg/mL AI/pen

Hypothesis: In subjects with episodic migraine, AMG 334 reduces the mean monthly migraine days from baseline, compared to placebo. **In the clinical home use (CHU) substudy, it is hypothesized that users will be able to administer a full dose of AMG 334 comparably using 2 pre-filled 70 mg/mL AIs/pens or 1 pre-filled 140 mg/mL AI/pen. No formal hypotheses will be tested in the CHU substudy.**

Primary Endpoint: Change from baseline in mean monthly migraine days. The mean monthly migraine days will be calculated using the monthly migraine days from each of the last three months (months 4, 5, and 6) of the double-blind treatment phase.

Secondary Endpoints:

Efficacy:

- Achievement of at least a 50% reduction from baseline in mean monthly migraine days over the last three months (months 4, 5, and 6) of the double-blind treatment phase
- Change from baseline in mean monthly acute migraine-specific medication treatment days over the last three months (months 4, 5, and 6) of the double-blind treatment phase

Safety:

- Adverse events
- Clinical laboratory values and vital signs
- Anti-AMG 334 antibodies

Clinical Home Use Substudy (During the OLTP) Endpoints:

Primary Endpoint: Subject-reported outcome of attempted full-dose administration at day 29 and day 57.

Secondary Endpoint: Subject incidence of adverse events, serious adverse events, and adverse device effects

Study Design: Phase 2, multicenter, randomized, stratified, double-blind, placebo-controlled, parallel-group study of subjects with episodic migraine. Approximately 459 subjects will be

randomized 2:1:2:2 to placebo, AMG 334 28 mg, AMG 334 70 mg, or AMG 334 140 mg, respectively. The randomization will be stratified by prior/current treatment with migraine prophylactic medication (current migraine prophylactic medication treatment vs prior migraine prophylactic medication treatment only vs no prior or current migraine prophylactic medication treatment).

Approximately 50 subjects will be enrolled in the AMG 334 20120309 CHU substudy to assess the subject's ability to self-administer 140 mg of AMG 334 for in-home use. Subjects will be randomized 1:1 to use either 2 pre-filled 70 mg/mL AIs/pens or 1 pre-filled 140 mg/mL AI/pen. Participation in the substudy is optional, and no additional samples will be collected for the substudy.

Sample Size: Approximately 459 randomized

Summary of Subject Eligibility Criteria: Adults 20 to 65 years of age with history of migraine with or without aura for ≥ 12 months and who experience ≥ 4 to < 15 migraine days per month with < 15 headache days per month.

For a full list of eligibility criteria, please refer to [Section 4.1](#) through [Section 4.2](#).

Amgen Investigational Product Dosage and Administration: Investigational product (IP) (ie, AMG 334 and placebo) will be dosed monthly (QM) by subcutaneous (SC) injection. Double-blind AMG 334 140 mg, AMG 334 70 mg, AMG 334 28 mg, or placebo will be administered during the 24-week double-blind treatment phase (ie, at day 1 and weeks 4, 8, 12, 16, and 20). **During the OLTP, AMG 334 70 mg or 140 mg QM SC will be administered, depending on the subject's visit completion status after institutional review board (IRB) approval of Protocol Amendment 2.**

Investigational product will be packaged in 3 mL clear glass vials for the double-blind treatment phase and 1 mL pre-filled syringes for the **OLTP**. For the vials and pre-filled syringes, AMG 334 will be presented as 70 mg/mL AMG 334. Placebo vials will be packaged to match AMG 334 but will not contain AMG 334.

Investigational product doses are fixed and will not be adjusted for individual subjects during the study. The anatomical sites for administration of investigational product are the upper arm, upper thigh, or abdomen.

See [Section 6.2.1](#) for further details.

Procedures: After signing informed consent, subjects will enter the screening phase. The screening phase is composed of an initial screening phase (up to 3 weeks) followed by a 4-week baseline phase. At the day 1 visit, eligible subjects will be enrolled (ie, randomized) into the 24-week double-blind treatment phase and will begin to receive double-blind investigational product QM SC. During the double-blind treatment phase, 3 SC injections are to be given for each investigational product administration (ie, at day 1 and weeks 4, 8, 12, 16, and 20) to maintain the dose-level blinding. At the week 24 visit, subjects will be entered into the 76-week **OLTP** and will begin to receive open-label AMG 334.

After IRB approval of Protocol Amendment 2, the 24-week double-blind treatment phase is followed by a 76-week OLTP with the dose determined by the subject's week 48 status:

- (1) **Subjects who have already completed the week 48 visit will continue to receive open-label AMG 334 70 mg QM SC (OL70) for a total of 76 weeks.**
- (2) **Subjects who have not yet completed the double-blind treatment phase and are not yet in the open-label phase will receive AMG 334 140 mg QM SC (OL140) upon entering the open-label phase and continue receiving open-label AMG 334 140 mg QM SC for 76 weeks.**
- (3) **Subjects who have not yet completed the week 48 visit but are in the open-label phase receiving AMG 334 70 mg QM SC must increase their dose to AMG 334 140 mg QM SC and continue receiving open-label AMG 334 140 mg QM SC until the week 100 visit (OL70-140) for a total open label phase duration of 76 weeks. The dose increase should be done at the first available opportunity, defined as the first**

visit after IRB approval of Protocol Amendment 2. Refer to [Table 3](#) for assessments to be collected at the visit of the dose increase and 12 weeks after the dose increase. At the time of the dose increase, the End of Open-label 70 mg electronic case report form (eCRF) page will need to be completed as subjects will be transitioning from 70 mg to 140 mg.

As a result of Protocol Amendment 2, there will be 3 possible dose sequences in the open-label phase, depending on completion of week 48 visit as noted above: (1) subjects receiving only AMG 334 70 mg QM SC in the open-label phase (OL70), (2) subjects receiving only AMG 334 140 mg QM SC in the open-label phase (OL140), and (3) subjects receiving both AMG 334 70 mg (for up to 24 weeks) and 140 mg QM SC (OL70-140).

Subjects assigned to receive AMG 334 140 mg QM SC during the open-label phase will not have the option to decrease open-label AMG 334 from 140 mg QM to 70 mg QM. A safety follow-up visit occurs 16 weeks after the last dose of investigational product. Subjects will use an electronic diary (eDiary) every day throughout the baseline phase and double-blind treatment phase and for the first 6 months and **between the week 72 and week 76 study visits and between the week 96 and week 100/early termination (ET) study visits** of the OLTP to report information about their migraine and non-migraine headaches and acute headache medication use. Subjects will have in-clinic study visits monthly after the week 4 visit.

For a full list of study procedures, including the timing of each procedure, please refer to [Section 7](#) and the Schedule of Assessments ([Table 2-Table 3](#), and [Table 4](#) for CHU substudy).

Statistical Considerations: The primary analysis will occur after all subjects have completed their week 24 visit (or discontinued from the study). The final analysis for the study will occur after all subjects have completed safety follow-up through week 112 or discontinued from the study. Using the treatment effect compared to placebo of -1.12 and -1.30 for the AMG 334 70 mg and 140 mg dose groups, respectively and a common standard deviation of 2.8 based on a Japan topiramate trial (www.clinicaltrials.gov), the planned sample size of 131 subjects in the placebo, 70 mg and 140 mg dose groups will provide 90% and 96% power for a two-sided test with significance level of 0.05 to show the superiority of AMG 334 70 mg and 140 mg compared to placebo, respectively. The proposed number of subjects in the 28 mg (n=66) dose group with the placebo (n=131), the 70 mg (n=131) and the 140 mg (n=131) dose groups is sufficient to demonstrate a dose-response using the Multiple Comparison Procedure–Modelling (MCP-Mod) analysis with the minimum power of 95% and provide the estimates of response in a Japanese population, using an assumed treatment effect of -0.55 for the AMG 334 28 mg dose group.

The continuous efficacy endpoints will be analyzed using a linear mixed effects model including treatment group, baseline value, stratification factor, scheduled visit, and the interaction of treatment group with scheduled visit, without any imputation of missing data. The primary endpoint will be tested for each AMG 334 treatment group compared to the placebo group using appropriate contrasts in a closed testing procedure. The mean change from baseline for each treatment group, and the treatment difference, 95% confidence intervals, and p-value will be reported. For all efficacy endpoints, nominal p-values will be provided for the comparisons between each AMG 334 treatment group vs the placebo group without multiplicity adjustment.

Dichotomous efficacy endpoints will be analyzed using a stratified Cochran-Mantel-Haenszel (CMH) test after the missing data are imputed as non-response. The odds ratio for each AMG 334 treatment group vs placebo group and associated 95% confidence intervals will be reported. As safety analyses, subject incidence of treatment-emergent adverse events will be tabulated by system organ class and preferred term by treatment group for the double-blind treatment phase. For the OLTP, **exposure**-adjusted subject incidence rate of treatment-emergent adverse events will be tabulated overall. Measurements of safety laboratory and vital sign data will be summarized over time and laboratory shift tables will be provided.

The proportion of subjects who administer a full dose of AMG 334 in home-use will be summarized by treatment group at CHU day 29 and day 57. Subject incidence of adverse

events, serious adverse events, and adverse device effects will be summarized by system organ class and preferred term for subjects enrolled in the CHU substudies.

[figure not shown]
For a full description of statistical analysis methods, please refer to [Section 10](#).

Sponsor: Amgen Inc.

Data Element Standards
Version/Date:

[figure not shown]
Version 4, 31 October 2013

Study Design and Treatment Schema for Subjects That Completed Week 48 Under Protocol Amendment 2 (OL70 subjects)

[figure not shown]
IP = investigational product; QM = monthly; SC = subcutaneous

Study Design and Treatment Schema for Subjects Still in the Double-blind Treatment Phase Protocol Amendment 2
(OL140 Subjects)

IP = investigational product; QM = monthly; SC = subcutaneous

Study Design and Treatment Schema for Subjects in the Open-label Phase AND Not Yet Completed W48 Under Protocol Amendment 2 (OL70-140 Subjects)

IP = investigational product; QM = monthly; SC = subcutaneous

Study Glossary

Abbreviation or Term	Definition/Explanation
ADE	Adverse device effect
AI/Pen	Autoinjector/pen
ALP	Alkaline phosphatase
ALT	Alanine transaminase
ANCOVA	Analysis of covariance
AST	Aspartate aminotransferase
BDI-II	Beck Depression Inventory-II
BIL	Bilirubin
BMI	Body mass index
BP	Blood pressure
BUN	Blood urea nitrogen
CBC	Complete blood count
CGRP	Calcitonin gene-related peptide
CHU	Clinical home use
C _{max}	Peak concentration
CMH	Cochran-Mantel-Haenszel
COAs	Clinical Outcome Assessments
cont	Continued
CPK	Creatine phosphokinase
CRF	Case report form
C-SSRS	Columbia-Suicide Severity Rating Scale
CTCAE	Common Terminology Criteria for Adverse Events
D	Day
Day 1 / Study Day 1	The first day that protocol-specified investigational product is administered to the subject
DBF	Dermal blood flow
DBTP	Double-blind treatment phase
DILI	Drug-induced liver injury
dL	Deciliter
DMC	Data Monitoring Committee
EC ₅₀	50% effective concentration
EC ₉₀	90% effective concentration
ECG	Electrocardiogram
eCRF	Electronic case report form

Abbreviation or Term	Definition/Explanation
EDC	Electronic data capture
eDiary(ies)	Electronic diary(ies)
End of study for individual subject	The last day that protocol-specified procedures are conducted for an individual subject
End of Study	The end of study date is defined as the date when the last subject across all sites is assessed or receives an intervention for evaluation in the study (ie, the last subject last visit), following any additional parts in the study (eg, long-term follow-up), as applicable.
Enrollment	Randomization of a subject into the double-blind treatment phase of the study via the Interactive Voice Response / Interactive Web Response System
EOS	End of study
E-R Analysis	Exposure-response analysis; mechanism-based modeling and simulation and statistical analyses based on individual pharmacokinetic exposure (eg, population pharmacokinetic modeling) and response, which may include biomarkers, pharmacodynamic effects, efficacy and safety endpoints.
ET	Early termination
ETO System	Electronic Trial Operations System; an electronic system that is used to facilitate the operations of a clinical trial through the collection of study-related data. The most common applications of an ETO system within a clinical trial are subject randomization and investigational product management. The term is synonymous with the industry term Interactive Voice Response (IVR) / Interactive Web Response (IWR) System.
FAS	Full analysis set
FSH	Follicle-stimulating hormone
F/U	Follow-up
g	Gram
GLP	Good Laboratory Practice
Hb	Hemoglobin
HCV	Hepatitis C virus
HDL	High-density lipoprotein
Headache	A migraine or non-migraine headache

Abbreviation or Term	Definition/Explanation
Headache Day	Any calendar day in which the subject experiences a qualified headache (initial onset, continuation or recurrence of the headache). A qualified headache is defined as: 
 • a qualified migraine headache (including an aura-only event that is treated with acute migraine-specific medication), or • a qualified non-migraine headache, which is a headache that lasts \geq 30 minutes and is not a qualified migraine headache, or • a headache of any duration for which acute headache treatment is administered.
HepBcAb	Hepatitis B Core Antibody
HepBsAg	Hepatitis B Surface Antigen
HIT-6	Headache Impact Test
HIV	Human immunodeficiency virus
ICF	Informed consent form
ICH GCP	International Conference on Harmonisation Tripartite Guideline on Good Clinical Practice
ICHD	The International Classification of Headache Disorders
ID	Identification
IFU	Instructions for use
IgG2	Immunoglobulin G2
IHS	International Headache Society
INR	International normalized ratio
IP	Investigational product (ie, AMG 334 and placebo)
IPIM	Investigational Product Instruction Manual
IRB	Institutional Review Board
IU	International unit
IVR/IWR System	Interactive Voice Response (IVR) / Interactive Web Response (IWR) System; telecommunication / web-based technology that is linked to a central computer in real time as an interface to collect and process information
K_d	Equilibrium dissociation constant
kg	Kilogram
Last IP Dose Date	The last date investigational product is administered
LDH	Lactate dehydrogenase
LDL	Low-density lipoprotein
LOCF	Last observation carried forward
M	Month
MAR	Missing at random

Abbreviation or Term	Definition/Explanation
MCH	Mean corpuscular hemoglobin
MCHC	Mean corpuscular hemoglobin concentration
MCP-Mod	Multiple Comparison Procedure–Modelling
MCV	Mean corpuscular volume
mg	Milligram
MI	Multiple imputation
Migraine Attack	An episode of any qualified migraine headache. The following rules will be used to distinguish an attack of long duration from two attacks, or to distinguish between attacks and relapses: 
 a) A migraine attack that is interrupted by sleep, or temporarily remits, and then recurs within 48 hours (ie, ≤ 48 hours between the start of the migraine attack to the time of the recurrence) will be considered as one attack and not two. b) An attack treated successfully with medication but with relapse within 48 hours (ie, ≤ 48 hours between the start of the migraine attack to the time of the recurrence) will be considered as one attack.
Migraine Day	Any calendar day in which the subject experiences a qualified migraine headache (onset, continuation, or recurrence of the migraine headache). A qualified migraine headache is defined as a migraine with or without aura, lasting for ≥ 30 minutes, and meeting at least one of the following criteria (a and/or b): 
 a) ≥ 2 of the following pain features: 
 • Unilateral • Throbbing • Moderate to severe • Exacerbated with exercise/physical activity b) ≥ 1 of the following associated symptoms: 
 • Nausea and/or vomiting • Photophobia and phonophobia 
If the subject took a migraine-specific medication (ie, triptan or ergotamine) during aura or to treat headache on a calendar day, then it will be counted as a migraine day regardless of the duration and pain features/associated symptoms.

Migraine-specific medications	Triptans and ergotamine-derivatives
mL	Milliliter
MNAR	Missing not at random
Monthly Headache Days	Number of headache days in any 28-consecutive day interval relative to study day 1
Monthly Migraine Days	Number of migraine days in any 28-consecutive day interval relative to study day 1
ng	Nanogram
NOAEL	No observed adverse effect level
NSAID	Nonsteroidal anti-inflammatory drug
OLTP	Open-label treatment phase

Abbreviation or Term	Definition/Explanation
PC	Product complaint
PCR	Polymerase chain reaction
PD	Pharmacodynamic
PE	Physical examination
PET	Positron emission tomography
PFS	Pre-filled syringe
pg	Picogram
PGt	Pharmacogenetics
PK	Pharmacokinetic
pM	Picomolar
Primary Completion	
The primary completion date is defined as the time when the last subject is assessed or receives an intervention for the final collection of data for the primary endpoint(s), for the purpose of conducting the primary analysis, whether the study concluded as planned in the protocol or was terminated early.
 
The primary completion date is the date when the last subject has completed the assessments for week 24 or is discontinued from the study.

PRN	As needed (pro re nata)
PRO	Patient-reported outcome
PT	Prothrombin time
QM	Monthly
rand.	Randomized / randomization
RBC	Red blood cell
RDW	Red blood cell distribution width
SAE	Serious adverse event
SC	Subcutaneous
SGOT	Serum glutamic-oxaloacetic transaminase; see AST
SGPT	Serum glutamic-pyruvic transaminase; see ALT
Source Data	Information from an original record or certified copy of the original record containing patient information for use in clinical research. The information may include, but is not limited to, clinical findings, observations, or other activities in a clinical trial necessary for the reconstruction and evaluation of the trial. Source data are contained in source documents (original records or certified copies) (ICH Guideline E6). Examples of source data include subject identification and randomization identification.
Study Day 1 / Day 1	The first day that protocol-specified investigational product is administered to the subject
TBL	Total bilirubin

Abbreviation or Term	Definition/Explanation
t_{max}	Time to peak concentration
True abstinence	To refrain from any sort of sexual activity that could involve the spill of an ejaculate, even if the spill does not occur
ULN	Upper limit of normal
WBC	White blood cell
Wk	Week
WOCBP	Woman/women of childbearing potential; any female who has experienced menarche and does not meet the criteria for "Women Not of Childbearing Potential"

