3.4 Number of Subjects

Participants in this clinical investigation shall be referred to as “subjects.”

Approximately 459 subjects will be enrolled (ie, randomized) into the study, with approximately 131 subjects assigned to placebo, approximately 66 subjects assigned to AMG 334 28 mg, approximately 131 subjects assigned to AMG 334 70 mg, and approximately 131 subjects assigned to AMG 334 140 mg.

To allow for 459 eligible subjects to be randomized, it is anticipated that approximately 800 will need to enter the initial screening phase, and approximately 600 will need to enter the baseline phase.

Approximately 50 subjects may participate in the CHU substudy.

The sample size justification is described in [Section 10.2](#).

Approximately 91 subjects will participate in the PK substudy.

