3.5 Replacement of Subjects

Subjects who are withdrawn or removed from treatment or the study will not be replaced.

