10.2 Sample Size Considerations

The primary endpoint is the change from baseline in mean monthly migraine days over the last three months (months 4, 5, and 6) of the double-blind treatment phase. Using the treatment effect compared to placebo of -1.12 and -1.30 for the AMG 334 70 mg and 140 mg dose groups, respectively and a common standard deviation of 2.8 based on a Japan topiramate trial (www.clinicaltrials.gov), the planned sample size of 131 subjects in the placebo, 70 mg and 140 mg dose groups will provide 90% and 96% power for a two-sided test with significance level of 0.05 to show the superiority of AMG 334 70 mg and 140 mg compared to placebo, respectively. The proposed number of subjects in the 28 mg (n=66) dose group with the placebo (n=131), the 70 mg (n=131) and the 140 mg (n=131) dose groups is sufficient to demonstrate a dose-response using MCP-Mod analysis with the minimum power of 95% and provide the estimates of response in a Japanese population, using an assumed treatment effect of -0.55 for the AMG 334 28 mg dose group.

Clinical Home Use Substudy

Approximately 50 subjects will be enrolled in to the CHU substudy. The following assumptions are made based on the minimum sample size of 50 subjects: 5% of subjects per treatment group discontinue IP and 90% of the remaining subjects respond that they administered a full dose. As such, the anticipated distribution of responses per treatment group at a planned visit would be 5% categorized as not attempting due to discontinuing IP, 85.5% responding that they administered a full dose, and 9.5% responding that they did not administer a full dose. The associated 95% confidence interval halfwidths with 25 subjects per group are

8.5%, 13.8%, and 11.5%, respectively. The anticipated 95% confidence interval half width for the difference between treatment groups in the proportion of subjects administering a full dose is 19.5%. The discontinuation rate is expected to be less than 5% and the rate of administering a full dose is expected to be greater than 90%, and therefore these calculations are anticipated to be lower bounds. Calculations were performed using nQuery Advisor 7.0.

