10.4.3 Primary Analysis

The objective of the primary analysis is to evaluate the efficacy and safety of AMG 334 in subjects with episodic migraine, compared to placebo, and to identify an optimal dose in Japanese population. The following hypothesis for the primary endpoint will be tested for each AMG 334 treatment group (140 mg, 70 mg, and 28 mg) compared to placebo using the linear mixed effects model:

- Clinical Hypothesis: In subjects with episodic migraine, AMG 334 reduces the mean monthly migraine days from baseline, compared to placebo

To maintain a family-wise type I error at 0.05, the pair-wise comparison will be tested in a sequential testing procedure in the order of AMG 334 140 mg vs. placebo, 70 mg vs. placebo and 28 mg vs. placebo. The lower dose group will be tested only when the higher dose group is considered statistically significant.

The primary analysis will be performed when the last subject completes the week 24 assessment or is discontinued from the study.

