3.2 Sample Size

The primary endpoint is the change from baseline in mean monthly migraine days over the last three months (months 4, 5, and 6) of the DBTP. Using the treatment effect compared to placebo of -1.12 and -1.30 for the AMG 334 70 mg and 140 mg dose groups, respectively and a common standard deviation of 2.8 based on a placebo-controlled dose-finding study of JNS019 (topiramate) in migraine patients (www.clinicaltrials.gov), the planned sample size of 131 subjects in the placebo, 70 mg and 140 mg dose groups will provide 90% and 96% power for a two-sided test with significance level of 0.05 to show the difference of AMG 334 70 mg and 140 mg compared to placebo, respectively. The proposed number of subjects in the 28 mg (n=66) dose group with the placebo (n=131), the 70 mg (n=131) and the 140 mg (n=131) dose groups is sufficient to demonstrate a dose-response using Multiple Comparison Procedure – Modelling (MCP-Mod) analysis with minimum power of 95% and provide estimates of response in a Japanese population, using an assumed treatment effect of -0.55 for the AMG 334 28 mg dose group.

Power calculations are derived through nQuery 7.0.

4. Study Endpoints and Covariates

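### The stated 90% power for 70 mg is that of a stand-alone test; under the plan's fixed sequence the same inputs give about 88%, before any loss of subjects

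*Protocol*

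**What the plan says.** The sample-size text appears in the protocol synopsis (Statistical Considerations), in Protocol 10.2 and in SAP 3.2. It takes a "treatment effect compared to placebo of -1.12 and -1.30 for the AMG 334 70 mg and 140 mg dose groups", with "a common standard deviation of 2.8 based on a Japan topiramate trial". From these, the protocol says that 131 subjects in each of the placebo, 70 mg and 140 mg arms "will provide 90% and 96% power for a two-sided test with significance level of 0.05 to show the superiority of AMG 334 70 mg" and of 140 mg. SAP 3.2 has the same result: "the planned sample size of 131 subjects in the placebo, 70 mg and 140 mg dose groups will provide 90% and 96% power".

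The 131 is the number randomised. Protocol 3.4 plans "approximately 131 subjects assigned to placebo, approximately 66 subjects assigned to AMG 334 28 mg" and 131 on each higher dose, and 131 + 66 + 131 + 131 = 459, the full enrolment target. Protocol 3.5 adds: "Subjects who are withdrawn or removed from treatment or the study will not be replaced".

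The doses are tested in a fixed order of 140 mg, 70 mg, 28 mg. Protocol 10.4.3 states the rule: "The lower dose group will be tested only when the higher dose group is considered statistically significant". Protocol 10.5.2 and SAP 5 and 10.1 repeat it. Neither sample-size section mentions the order, and neither gives an allowance for loss in the primary comparison.

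**The concern.** Power to show superiority of 70 mg should be the probability that the planned procedure ends with 70 mg declared superior. Under the sequence that requires two significant results, 140 mg and then 70 mg. The probability of both cannot exceed the probability of the 70 mg test alone, so a stand-alone figure overstates it.

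Separately, the calculation takes the number randomised as the number analysed. The efficacy analysis set (Protocol 10.1.2, SAP 7.2) leaves out subjects with no dose or no usable double-blind month of diary data, and the primary model does not impute. If some subjects contribute nothing, both powers fall below the stated figures.

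At stake is how the trial's chance of establishing 70 mg is described. The same joint success also controls a later step: Protocol 10.5.2 begins the MCP-Mod dose-response analysis only after both 70 mg and 140 mg have beaten placebo.

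**Working it through.** **Inputs.** Effects of 1.12 (70 mg) and 1.30 (140 mg) days in absolute value, SD 2.8, n = 131 per arm and two-sided alpha 0.05, all from Protocol 10.2. The testing order is from Protocol 10.4.3. The placebo arm is shared by both comparisons.

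**Step 1: reproduce the stated figures.**

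- Standard error of a difference: SE = SD × √(2/n) = 2.8 × √(2/131) = 0.346.
- 70 mg: 1.12/0.346 = 3.237. Power ≈ Φ(3.237 − 1.960) = Φ(1.277) = 89.9%. The non-central t gives 89.7%.
- 140 mg: 1.30/0.346 = 3.758. Power ≈ Φ(3.758 − 1.960) = Φ(1.798) = 96.4%. The non-central t gives 96.3%.

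These are the printed 90% and 96%. They need all 131 randomised subjects analysed, and no gate on 70 mg.

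**Step 2: apply the sequence.** With equal arms and a common placebo group, the two test statistics have correlation 0.5: the placebo variance is half the variance of each difference. Power for 70 mg is then

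P(both significant) = Φ₂(1.277, 1.798; ρ = 0.5) = 87.8%.

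Simulation agrees: 87.7% with a variance pooled over all four arms, and 87.5% with separate pairwise t tests. The chance of not establishing 70 mg is therefore 1 − 0.878 = 12.2%, about 1 in 8, against the 1 in 10 that the text implies. The 140 mg test comes first, so its power does not change.

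**Step 3: sensitivity to loss (assumption).** The documents give no rate at which subjects will provide no primary-endpoint data. The table reduces n to 131 × (1 − loss) in every arm, which treats each lost subject as contributing nothing.

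| Assumed complete loss | n per arm | 70 mg alone | 140 mg | 70 mg in sequence |
|---|---|---|---|---|
| 0% | 131 | 89.7% | 96.3% | 87.8% |
| 5% | 124.4 | 88.2% | 95.4% | 85.9% |
| 10% | 117.9 | 86.4% | 94.4% | 83.7% |

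Single tests use the non-central t, and the last column uses the bivariate normal. Simulated t tests for the last column give 87.5%, 85.4% and 83.4% at n = 131, 124 and 118.

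Only the first row follows from the documents alone.

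**The case against.** **The stated figures are correct for what they describe.** The text gives power "for a two-sided test with significance level of 0.05", which is a pairwise statement, and the sequence is set out fully elsewhere. This stands: there is no slip of arithmetic. What is missing is a statement that 90% is not the power of the planned procedure for 70 mg.

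**Removing whole subjects is pessimistic.** One usable month puts a subject in the efficacy set. A month counts with 14 diary days and is prorated (Protocol 10.1.1.5, SAP 9.3). Subjects who stop treatment are followed to the end of the double-blind phase (Protocol 6.2.1.2), and the mixed model uses every observed month. This also stands, and it is why the 5% and 10% rows are only a sensitivity range.

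**Baseline adjustment may restore the power.** The primary model includes the baseline value, and the calculation takes no credit for it. Suppose 2.8 is an unadjusted SD and the baseline value has correlation r with change, so that the SD falls to 2.8 × √(1 − r²). Then r = 0.25 brings sequential 70 mg power back to 90.0% with no loss. With r = 0.4 it is 91.8% at 5% loss and 90.2% at 10%. The documents do not give r or say whether 2.8 is already adjusted, so this is as much an assumption as the loss rate.

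**The planning effects may be conservative.** Protocol 2.3 reports a global Phase 3 trial with differences from placebo of −3.23 − (−1.83) = −1.40 for 70 mg and −3.67 − (−1.83) = −1.84 for 140 mg. With SD 2.8 these give sequential 70 mg power of 98.1% with no loss and 96.9% at 10% loss. This lowers the practical stakes. It does not make 90% the right figure for the effects the plan chose.

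**What a reader might wrongly infer.** It is tempting to conclude that power for 70 mg is really 84%, or that the trial has a 1 in 6 chance of missing it. That needs 10% complete loss in every arm, and the documents give no such rate. The safety percentages of the sponsor's earlier Phase 2 trial (165 at 51.7%, 82 at 53.6%) imply about 319 + 153 = 472 of 483 randomised, a shortfall of 2.3%. Those are adverse-event denominators from another trial, not a count of missing endpoint data, so they do not supply the rate either.

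**Conclusion.** The point holds as a limit on what the stated power means. The 90% for 70 mg is a pairwise power. Through the plan's own sequence it is about 88% at the planning effects, with all 131 per arm analysed and a shared placebo arm. The shortfall of about 2 points needs no outside assumption. The 96% for 140 mg is right at 131 analysed.

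The lack of any allowance for loss is also real, but its size cannot be fixed from the documents. The range of about 86% to 84% for 70 mg, and 95% to 94% for 140 mg, depends on assumed complete losses of 5% to 10% and leaves out any recovery from partial data or baseline adjustment.

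The effect is modest and gives no reason to enlarge the trial or to change the analysis. Nor does it show that the trial is underpowered.

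**What to change.** Keep the sample size and the testing order. In the synopsis, Protocol 10.2 and SAP 3.2, restate the power along these lines:

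> With 131 subjects analysed per arm, pairwise power against placebo is 90% for 70 mg and 96% for 140 mg. Because 70 mg is tested only if 140 mg is significant, power to establish 70 mg through the fixed sequence is about 88%. These figures include no loss of subjects and no gain from covariate adjustment.

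If the sponsor wishes to show a loss scenario, it should be labelled as an assumption, with its rate and basis given, and should say whether partial data and baseline adjustment are credited.

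The cost is wording in three places and a slightly less favourable figure for 70 mg. No additional subjects are needed.
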